#### Most Prevalent Grade 2-4 Adverse Events in the Everolimus Arm of EVEREST

Among all Randomized Patients on the Everolimus Arm Who Received Any Study Drug

Toxicity	% of Evaluable with Grade 2-4
High Cholesterol	10%
Fatigue	19%
Hyperglycemia	14%
Hypertriglyceridemia	27%
Oral mucositis	35%
Rash	14%
Composite Endpoints	
Any Toxicity Grade 2-4	87%
Any Toxicity Grade 3-4	46%
Refusal/Tox within first 3 months	25%
Refusal/Tox within first 6 months	41%
Refusal/Tox prior to 12 months	52%

In order to simplify power calculations related to everolimus blood concentrations, we will assume the distribution of values will be divided into quartiles. The following table indicates the minimally detectable odds ratio that could be detected between the lowest and highest quartile in terms of predicting an adverse event. A range of prevalences are illustrated below to show how the effect size changes with the prevalence of the adverse event.

Minimally Detectable Odds Ratio for Highest versus Lowest Quartile of everolimus in the blood, assuming 80% Statistical Power and a Two-sided Alpha=0.05.

	Prevalence of Adverse Event Endpoint				
	10%	20%	30%	40%	50%

Q4 vs. Q1 of everolimus concentration	6.5	3.6	3.0	2.7	2.7
---------------------------------------	-----	-----	-----	-----	-----

An individual adverse event that is only reported by 10% of patients who receive everolimus will need to have a very strong association with concentration of everolimus in the blood (odds ratio 6.5 between highest and lowest concentration) in order to be detected as a significant association. An association of any Grade 3-4 toxicity only needs to be in the range of an odds ratio of 2.7 to be detectable.

For patients who have had a dose reduction of protocol therapy at the time of their blood draw, we will handle this in two ways. First, we will just analyze the everolimus level as it appears in the blood and ignore the dose received, and the second approach will standardize the amount of everolimus in the blood conditional on the dose of drug taken.

Logistic regression will be used to model adverse event outcomes with everolimus blood concentration as a predictor, adjusting for other stratification factors and age, gender and race.

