9.0 STUDY CALENDAR

√

REQUIRED STUDIES	PRE STUDY	Cycle 1						Cycle 2		Cycle 3 §		Off Treat F/U Prior to Recurrence	Recurrence	Off Treat F/U After Recurrence
		WK 1	WK 2	WK 3	WK 4	WK 5	WK 6	WK 7 ----->12	WK	WK 13 ----->18	WK			
PHYSICAL														
History and Physical Exam	X*	XЯ			X			X		X		X	X	X
Hepatitis B/C Screening †	X													
Weight and Performance Status	X	XЯ						X		X				
Recurrence Assessment ¶ Ж											X	X¶	X	
Toxicity Notation Ω		X	X	X	X	X	X	X		X				
Review Intake Calendar								X		X				
LABORATORY														
WBC/Differential /Platelets	X							X		X				
Hemoglobin	X							X		X				
Bilirubin	X							X		X				
SGOT and SGPT	X							X		X				
Serum Creatinine or Calculated Creatinine Clearance	X							X		X				
Alkaline Phosphatase	X							X		X				
Fasting Glucose, Cholesterol and Triglycerides	X							X		X				
HBV DNA or HCV RNA-PCR Δ								X		X				

Study Calendar continued on next page. Click here for [footnotes](#).

√

REQUIRED STUDIES	PRE STUDY	Cycle 1						Cycle 2		Cycle 3 §		Off Treat F/U Prior to Recurrence	Recurrence	Off Treat F/U After Recurrence
		WK 1	WK 2	WK 3	WK 4	WK 5	WK 6	WK 7 ----->12	WK 13 ----->18	WK	WK			
SPECIMEN SUBMISSION ¶														
Archived Tumor Specimen	X													
Buffy Coat and Plasma Specimens	X							X		X		X	X	
Whole Blood for Trough Levels	X							X		X		X		
X-RAYS AND SCANS														
CT Scan of Chest/Abdomen/Pelvis £ ¶	X										X £ ¶	X	X	
Bone Scan ¶	X¶											X¶		
TREATMENT (see Section 7.0 for details)														
Everolimus/Placebo		X ----->X												

Click here for [footnotes](#).

FOOTNOTES:

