If 936 of patients randomized to this trial provide a usable tissue sample for these translational objectives, and the prevalence of the biomarker of interest is 20%, then we will have reasonable power (80%) to detect a hazard ratio of approximately 0.50 for those with a marker compared to a HR of 1.0 for those without the marker ( $1.0/0.50 = 2.00$ ). Frequency and severity of adverse events and proximity to sample collection will be correlated with steady-state  $C_{min}$ . Assuming 90% of those randomized to everolimus will submit one or more serum samples, we will have approximately 526 subjects to analyze.

Initially, correlations of adverse events and the  $C_{min}$  in closest proximity to the adverse event will be explored in a manner analogous to multiple t-tests. Logistic regression modeling will be used to assess whether  $C_{min}$  is a predictor for the presence of the adverse events after adjusting for other patient and disease covariates. Proportional odds (PO) models may be used to model severity of an adverse event in ordinal categories, if the PO modeling assumption is supported by the data.

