#### 11.5 Pharmacokinetic Analysis of Blood Samples

For the pharmacokinetic analysis of blood samples, we will use blood samples that were collected at Week 7 or Week 13 and the patient must have been randomized to the everolimus arm and be receiving protocol treatment at the time of the blood draw. At the time of the on-study analysis in the winter of 2014, there were 83 patients with one blood draw and 165 with two for a total of 248 patients. For those with two on-treatment measurements, the average of the two will be used for analysis to reduce measurement error bias.

The purpose of the analysis is to correlate everolimus blood concentrations from early blood draws with the experience of adverse events by the patients, both in terms of general grades of toxicities but also by specific adverse events that have been more frequently reported on the everolimus arm. The following calculations assume a PK analysis will be conducted prior to accrual completion in order to gain insight into the relationship between blood levels of the study drug and adverse events. We anticipate there will be more samples to evaluate later in the trial and so effect sizes will be smaller with larger sample sizes.

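### Section 11.5 should analyse the full grade for cholesterol, glucose and triglycerides; a Grade 2-4 yes/no outcome loses about 66%, 59% and 45% of the information

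*Combined protocol and SAP*

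**What the plan says.** Section 11.5 relates everolimus blood concentration at Week 7 or Week 13 to toxicity, both as general grades and as specific adverse events. At the winter 2014 count, "there were 83 patients with one blood draw and 165 with two for a total of 248 patients"; more are expected later. The only model named is: "Logistic regression will be used to model adverse event outcomes with everolimus blood concentration as a predictor". It adjusts for the stratification factors, age, gender and race.

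The outcome table lists Grade 2-4 rates for six toxicities, including high cholesterol 10%, hyperglycemia 14% and hypertriglyceridemia 27%. For power, "we will assume the distribution of values will be divided into quartiles", and detectable odds ratios for the highest versus lowest quartile are tabulated by event prevalence, "assuming 80% Statistical Power and a Two-sided Alpha=0.05". The section accepts that an event seen in 10% of patients "will need to have a very strong association with concentration of everolimus in the blood" (odds ratio 6.5).

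The study calendar (9.0) requires "Fasting Glucose, Cholesterol and Triglycerides" pre-study and in Cycles 2 and 3, the cycles in which the trough sample is drawn, and at the same intervals to Cycle 9. Section 11.4, on the same question of trough level and adverse events, adds: "Proportional odds (PO) models may be used to model severity of an adverse event in ordinal categories", if the data support the assumption. Section 11.5 does not repeat this.

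**The concern.** Section 11.5 averages two concentrations per patient to limit measurement error in the predictor. On the outcome side, three quantities that are measured as numbers appear to be reduced to yes or no. A patient just below the Grade 2 limit then counts the same as one with a normal result, and a patient far above it counts the same as one just over it.

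These three toxicities are also three of the five side effects named in objective 1.3b. The Background hopes that trough levels will yield an upper threshold for this population. If the analysis is weak, a null result could be read as no relation with concentration when the outcome was simply coarse.

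**Working it through.** **Inputs.** 248 patients, so 62 per quartile; two-sided alpha 0.05; 80% power; Grade 2-4 prevalences p = 0.10, 0.14 and 0.27 (all from 11.5). Any-grade rates of 76% (cholesterol), 50% (glucose) and 71% (triglycerides) come from the advanced renal carcinoma trial described in the Background.

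**1. The plan's own table.** Compare quartile 4 with quartile 1 (62 versus 62), with overall prevalence fixed, log-odds linear across quartiles, and unpooled variance:

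power = Φ{(p4 − p1)/√[p1(1−p1)/62 + p4(1−p4)/62] − 1.96}

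At 10% prevalence and odds ratio 6.5, p1 = 0.035 and p4 = 0.190, and power is 80.6%.

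| Prevalence | 10% | 20% | 30% | 40% | 50% |
|---|---|---|---|---|---|
| Stated odds ratio | 6.5 | 3.6 | 3.0 | 2.7 | 2.7 |
| Recomputed | 6.39 | 3.62 | 3.00 | 2.77 | 2.71 |

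The table reproduces to within rounding and method.

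**2. Information kept by a yes/no cut.** For a normal value, a weak association and one value per patient, the fraction kept is E = φ(z)²/[p(1−p)], where z is the normal quantile that leaves p above it.

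| | p | φ(z) | E | Lost | E × 248 |
|---|---|---|---|---|---|
| Cholesterol | 0.10 | 0.1755 | 0.0308/0.0900 = 0.342 | 66% | 85 |
| Glucose | 0.14 | 0.2226 | 0.0496/0.1204 = 0.411 | 59% | 102 |
| Triglycerides | 0.27 | 0.3306 | 0.1093/0.1971 = 0.555 | 45% | 138 |

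Even a 50/50 split keeps only 0.637, so no yes/no cut of a normal value loses less than 36%.

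**3. Power at a true correlation r = 0.20.** Power = Φ{atanh(r√E)·√(n−3) − 1.96}, with E = 1 for the uncut value. For cholesterol at n = 248, r√E = 0.117, and 0.1175 × 15.65 − 1.96 = −0.12, so power is 45%.

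| n | Uncut | Cholesterol | Glucose | Triglycerides |
|---|---|---|---|---|
| 248 | 89% | 45% | 52% | 65% |
| 526 (projected in 11.4) | >99% | 77% | 84% | 93% |

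A simulation at n = 248 (1,000 data sets per setting) agrees: 88-91% uncut, and 45%, 52% and 66% cut.

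**4. How much of the 6.5 is due to the cut.** The quartile contrast uses 124 of the 248 patients, whereas the planned model uses concentration as predictor. If concentration enters per SD, the detectable coefficient at p = 0.10 is 2.80/√(248 × 0.10 × 0.90) = 0.593. The means of the top and bottom quarters of a normal variable lie 2.54 SD apart, so this is an odds ratio of exp(0.593 × 2.54) ≈ 4.5. Part of the 6.5 therefore comes from the quartile simplification.

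**5. What ordinal grade recovers.** With categories 0, 1 and 2 or more, E = Σ(φ_lower − φ_upper)²/π over the categories, where π is the category share. For cholesterol the shares are 0.24, 0.66 and 0.10, and the densities at the two cuts are 0.3109 and 0.1755:

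0.3109²/0.24 + (0.3109 − 0.1755)²/0.66 + 0.1755²/0.10 = 0.403 + 0.028 + 0.308 = 0.74

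The same sum gives 0.76 for glucose and 0.81 for triglycerides. The range is 74-81% kept, against 34-55% for the yes/no cut.

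**The case against.** The strongest reply is that 11.5 asks about adverse events during treatment, not about laboratory values at one or two early visits. A fasting value at Week 7 or Week 13 misses later events. Section 8.4b also calls for drug treatment of Grade 2 or greater lipid elevations, so later values are lowered selectively in the most affected patients, while a recorded event remains. Section 14.4 lists Treatment and Adverse Event Forms each cycle but does not show that numeric on-treatment results are submitted. The planned covariates include no pre-study laboratory value. All of this stands. A reader might infer that a continuous analysis should replace the event model; the documents do not support that.

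A reader might also infer that a moderate effect would usually be missed. That depends on the interim count of 248: at 526 patients the yes/no powers are 77% to 93%. The proportion lost does not change with sample size.

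The sponsor could add that proportional odds modelling is already in 11.4. It is there only as an option, and 11.5, which gives the specific plan, names logistic regression alone.

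**Conclusion.** The point holds as an inexpensive improvement to a translational analysis. For cholesterol, glucose and triglycerides, a Grade 2-4 yes/no outcome loses about 66%, 59% and 45% of the information in the underlying value.

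This rests on five assumptions: a normal value (for example after log transformation), a weak association, one value per patient, prevalences among all treated everolimus patients that also apply to the pharmacokinetic set, and Grade 2-4 as the modelled outcome. The last is inferred from the prevalence table; 11.5 speaks only of adverse event outcomes.

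The ordinal gain further assumes that the any-grade rates from advanced disease carry over and that Grade 1 is recorded. With fewer Grade 1 events the gain shrinks towards the yes/no figures.

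Two stronger readings are not supported. The power table contains no arithmetic error, and the odds ratio of 6.5 is not solely a cost of the cut. Recurrence-free and overall survival are not affected.

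**What to change.** In 11.5, for these three toxicities:

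- State the outcome, and make the main model a proportional odds model of the full 0-4 grade from the Adverse Event Form on concentration, with the planned covariates. The form is already submitted each cycle, and the analysis stays on the adverse-event question.
- Keep the Grade 2-4 logistic model as the clinical summary.
- If numeric on-treatment values are in the database, add a supportive linear model of the log fasting value at Week 7 or Week 13 on log concentration, adjusted for the pre-study value as well as the planned covariates. Pre-specify how values taken after lipid- or glucose-lowering treatment are handled, for example by a sensitivity analysis that excludes them.

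The cost is SAP wording and a little more analysis, with no new visits. The proportional odds assumption has to be checked, and the supportive model will not capture later events.

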## **5.0 ELIGIBILITY CRITERIA**

Each of the criteria in the following section must be met in order for a patient to be considered eligible for registration. Use the spaces provided to confirm a patient's eligibility. For each criterion requiring test results and dates, please record this information on the **S0931** Prestudy Form and submit to the Data

Operations Center in Seattle (see [Section 14.0](#)). Any potential eligibility issues should be addressed to the Data Operations Center in Seattle at [[contact]](mailto:[contact]) or [name] prior to registration.

In calculating days of tests and measurements, the day a test or measurement is done is considered Day 0. Therefore, if a test is done on a Monday, the Monday 2 weeks later would be considered Day 14. This allows for efficient patient scheduling without exceeding the guidelines. **If Day 14, 28, 42, or 84 falls on a weekend or holiday, the limit may be extended to the next working day.**

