Grade 3 febrile neutropenia (not life-threatening)	Interrupt everolimus until resolution of fever and neutropenia to Grade $\leq 1$ . Hold further everolimus until the ANC $\geq 1,500/mm^3$ and fever has resolved. Then resume everolimus at one lower dose level. If febrile neutropenia recurs, discontinue everolimus.
Grade 4 febrile neutropenia (life-threatening)	Discontinue everolimus.

\* Grade 2-3 hyperlipidemia (hypercholesterolemia and/or hypertriglyceridemia) should be managed using medical therapies (see [Section 8.4b](#)).

If a patient requires a dose delay of > 21 days for pneumonitis or > 28 days for any other reason from the intended day of the next scheduled dose, then the patient must be removed from the protocol treatment.

a. Hematological Toxicity

No dose adjustments are recommended for anemia. The treating physician may hold everolimus for anemia if it is felt to be in the best interest of the patient. Aranesp (darbepoetin alfa) and Procrit (epoetin alfa) are not indicated for anemia. If patient does not recover after 28 days of holding drug then the patient must be removed from treatment.

Growth factors (e.g. G-CSF, GM-CSF, erythropoietin, platelet growth factors, etc.) are not to be administered prophylactically but may be prescribed by the treating physician for rescue from severe hematologic events.

b. Hyperlipidemia and Hyperglycemia

Treatment of hyperlipidemia should take into account the pre-treatment status and dietary habits. Blood tests to monitor hyperlipidemia must be taken in the fasting state. Grade 2 or greater hypercholesterolemia (> 300 mg/dL or 7.75 mmol/L) or Grade 2 or greater hypertriglyceridemia (> 300 mg/dL - 500 mg/dL; >3.42 mmol/L- 5.7 mmol/L) should be treated with a 3-hydroxy-3-methyl-glutaryl (HMG)-CoA reductase inhibitor (e.g., atorvastatin, pravastatin) or appropriate lipid-lowering medication, in addition to diet. Patients should be monitored clinically and through serum biochemistry for the development of rhabdomyolysis and other adverse events as required in the product label/data sheets for HMG-CoA reductase inhibitors.

Note: Concomitant therapy with fibrates and an HMG-CoA reductase inhibitor is associated with an increased risk of a rare but serious skeletal muscle toxicity manifested by rhabdomyolysis, markedly elevated creatine phosphokinase (CPK) levels and myoglobinuria, acute renal failure and sometimes death. The risk

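### The Section 11.5 exposure-toxicity model omits the pre-study value of the laboratory test being graded, and the plan does not say that a laboratory event must be new or worse than baseline (minor)

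*Combined protocol and SAP*

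**What the plan says.** - **Section 11.5, model.** Adverse-event outcomes are modelled by logistic regression with "everolimus blood concentration as a predictor, adjusting for other stratification factors and age, gender and race". Per Section 6.0, the stratification factors are risk group, histology and performance status. No laboratory value is named.
- **Section 11.5, patients.** Only everolimus-arm patients with an on-treatment Week 7 or Week 13 sample are used. At the 2014 count "there were 83 patients with one blood draw and 165 with two for a total of 248 patients".
- **Section 11.5, events.** The table of frequent Grade 2-4 events includes high cholesterol (10%), hyperglycemia (14%) and hypertriglyceridemia (27%). It covers all everolimus patients who took any study drug and states no rule on baseline grade.
- **Section 11.4.** The companion Cmin models test Cmin "after adjusting for other patient and disease covariates", which are not specified.
- **Section 8.4b.** The Grade 2 lipid limits are absolute values: "Grade 2 or greater hypercholesterolemia (> 300 mg/dL or 7.75 mmol/L) or Grade 2 or greater hypertriglyceridemia", the latter starting above 300 mg/dL.
- **Criterion 5.3j.** A patient is excluded for fasting cholesterol above 300 mg/dL AND fasting triglycerides above 2.5 x ULN. It also asks for optimal lipid control before registration, without a numeric definition.
- **Availability.** The Section 9.0 calendar requires "Fasting Glucose, Cholesterol and Triglycerides" pre-study, and Section 5.0 says "For each criterion requiring test results and dates, please record this information on the" Prestudy Form.

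**The concern.** For a laboratory toxicity, the pre-study value of the same test is usually among the strongest predictors of the on-treatment value. A model that leaves it out carries avoidable noise. If baseline happens to be related to trough level, it also carries confounding.

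For the two lipid events there is a second gap. Because 5.3j needs both lipids to be high, a patient with one lipid inside its limit has no numeric ceiling on the other at entry, apart from the undefined request for optimal control. Such a patient can already meet the protocol's own Grade 2 limit before the first dose, and nothing in 11.4 or 11.5 says whether that is an event. The analysis is confined to the everolimus arm, so no placebo comparison offsets pre-existing abnormality.

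At stake is the exposure-toxicity relation for laboratory events that objective 1.3b names. Section 2.0 hopes that relation will yield an upper threshold level. Events already present before treatment would raise the low-exposure event rate and flatten the curve.

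**Working it through.** **1. Inputs.** From Section 11.5: 248 patients, so 248/4 = 62 per quartile; "assuming 80% Statistical Power and a Two-sided Alpha=0.05"; event rates of 27% (hypertriglyceridemia) and 10% (high cholesterol). *Assumptions:* these rates, given for all treated patients, also hold in the PK subset; a share b of patients is at Grade 2 on entry (not in the documents, so a range is shown); and b is unrelated to blood level.

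**2. Reproducing the plan's table.** Take log-odds linear over quartiles, logit p_k = a + (k-1) ln(OR)/3, with the mean of p_1 to p_4 equal to the stated prevalence. Compare Q4 with Q1 by the unpooled normal test:

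power = Φ{ (p4 - p1) / √[(p1(1-p1) + p4(1-p4))/n] - 1.96 }

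Example, 30% and OR 3.0: p1 = 0.193, p4 = 0.418; 0.225/0.0802 = 2.80; Φ(0.84) = 80%.

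| Prevalence | 10% | 20% | 30% | 40% | 50% |
|---|---|---|---|---|---|
| Stated detectable OR | 6.5 | 3.6 | 3.0 | 2.7 | 2.7 |
| Recomputed | 6.39 | 3.62 | 3.00 | 2.77 | 2.71 |

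The table stands. At 27% the same method gives a detectable OR of 3.12.

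**3. Effect of counting baseline Grade 2 patients, hypertriglyceridemia.** The rate among patients not yet at Grade 2 is e = (0.27 - b)/(1 - b). It is split over quartiles with OR 3.12, and the observed quartile rate is b + (1 - b)p_k. For b = 5%: e = 0.22/0.95 = 0.232; p1 = 0.140, p4 = 0.337; observed 0.183 and 0.370; observed OR = (0.370/0.630)/(0.183/0.817) = 2.62. For the last column these patients are removed, so n = 62(1 - b).

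| b | Share of counted events (b/0.27) | Observed OR | Power, counted | Power, removed |
|---|---|---|---|---|
| 0 | 0% | 3.12 | 80% | 80% |
| 2% | 7% | 2.92 | 75% | 78% |
| 5% | 19% | 2.62 | 66% | 73% |
| 10% | 37% | 2.18 | 49% | 64% |

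**4. High cholesterol (10%, detectable OR 6.39).** b = 2% gives an observed OR of 4.19, with power 63% counted and 71% removed. b = 5% gives 2.42, with 31% and 51%; but then half of all reported events (0.05/0.10) would pre-date treatment, so this is an outer bound. Section 11.5 already concedes that a 10% event needs an "odds ratio 6.5 between highest and lowest concentration".

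**5. More samples.** Section 11.4 projects about 526 patients, 526/4 ≈ 131 per quartile. For hypertriglyceridemia at b = 5% the powers become 93% counted and 96% removed.

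**6. The covariate itself.** Steps 3 to 5 concern the event definition; adding a covariate does not change who is an event. A separate simulation kept every baseline Grade 2 patient as an event and only added the pre-study value to the model (248 patients, b of 2% to 10%, assumed baseline-to-treatment correlation 0.4 to 0.6). Power rose by about 4 to 19 points. That range depends on the assumed correlation, which the documents do not give.

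**The case against.** The strongest reply is that the documents nowhere say pre-existing abnormalities are scored as events. Section 2.0 speaks of the incidence of these toxicities, which ordinarily means new occurrence, and the calendar's toxicity notation starts in Week 1 with no pre-study entry. This stands: a reader might infer that patients entering at Grade 2 are counted as everolimus toxicity whatever their blood level, but the text supports only that the event definition is unstated.

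Other objections also stand:
- **Grade 2 throughout.** A reader might suppose such a patient stays at Grade 2. Section 8.4b calls for lipid treatment at that grade, so it may fall; it may also rise with exposure.
- **Free entry at Grade 2.** The optimal-control sentence in 5.3j may keep the share small, even though it sets no number.
- **Glucose.** Criterion 5.3k excludes on fasting glucose alone, and the documents give no Grade 2 glucose limit. Entry at Grade 2 is shown for the two lipids only; for glucose just the missing covariate applies.
- **Direction.** Dilution toward 1 assumes that baseline lipids are unrelated to trough. If they are related, bias could go either way, which is a further reason to adjust.
- **Setting.** The 248 patients are an early snapshot, quartiles serve only the power calculation, and the planned model uses blood concentration as the predictor.

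None of this puts the pre-study value into the 11.5 covariate list. The unspecified covariates in 11.4 permit it there but do not require it.

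**Conclusion.** The concern holds as a minor point. The 11.5 model omits an available and relevant covariate, and 11.4 and 11.5 leave open whether a laboratory abnormality present at entry is an event. If such patients are counted, the loss for hypertriglyceridemia at 62 per quartile runs from small (b = 2%: OR 3.12 seen as 2.92, power 75%) to material (b = 10%: 2.18, power 49%). The true share is unknown, and the loss is smaller with more samples. These figures rest on an assumed b, on independence of baseline and trough, and on the quartile approximation.

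Two further inferences would go too far. The detectable-odds-ratio table is not wrong; it reproduces. And the point does not reach the primary endpoint, overall survival or the between-arm toxicity comparison; it is confined to a secondary translational analysis within the everolimus arm.

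**What to change.** In Section 11.5, for cholesterol, triglycerides and glucose:

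1. Count an event only if the on-treatment grade is worse than the pre-study grade of the same test.
2. Add the pre-study fasting value of that test as a covariate in its logistic model.

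Apply both rules to the Cmin models in Section 11.4, replacing the open reference to patient and disease covariates for these endpoints. Both parts are needed: the covariate alone leaves baseline Grade 2 patients as events, and the event rule alone leaves the remaining baseline variation unadjusted.

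The cost is analysis-plan wording, one more term per model and slightly lower event rates for these endpoints. No new data are needed, because the values are already required pre-study. Reporting the share of patients at Grade 2 on entry for each lipid would show how much the rule matters.
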